5 STUDY SCHEDULE

It is important to note that consent, scales, and experiments will all take place in a private room. Any phone calls will take place in a private lab environment as well.

5.1 SCREENING

The screening process will involve a telephone call with the potential participant to inform of expectations and determine eligibility. A researcher will conduct a screening with each participant prior to scheduling the first session. If a participant is determined to be ineligible, contact information and screening question answers will be retained to avoid rescreening the participant. All data retained will be deidentified.

5.2 STIMULATION SESSIONS

Participants will undergo four sessions with the same procedure; the only change will be the stimulation condition. In the initial session, participants will have the procedure explained and reminded of their expectations and rights (informed consent). After obtaining consent, a urine drug test and pregnancy screening will be administered. Sessions 2, 3, and 4 will be the same as session 1, except there will be no CF-tACS stimulation during session 1.

5.4.1 SESSION 1

In the initial session, participants will be explained the procedure and reminded of their expectations and rights (informed consent). After obtaining consent, a urine drug test and pregnancy screening will be administered.

- Preparation - Once a negative pregnancy test and negative drug test are confirmed, the stimulation electrodes, EEG net, ECG electrodes and respiration belt will be applied.
- Questionnaires - The participant will fill out a series of questionnaires pertaining to self-reported handedness, affect, behavioral traits and sleep quality.
- Saliva collection - Saliva will be collected for BDNF genotyping and sex hormone level measurement.
- Resting state EEG – Participant will be asked to relax with eyes open and EEG will be collected simultaneously
- Practice cognitive tasks - The participant will perform a shortened version of the cognitive tasks as practice from which baseline performance will be assessed.

· Following the practice, the participant will receive 40 minutes of either verum CF-tACS or sham CF-tACS stimulation, depending on the randomized condition. During the stimulation, the following procedures will be followed

A. Cognitive Control Task – Participant will perform a cognitive control task for 5 minutes. CF-tACS will be delivered during these 5 minutes. There will be no CF-tACS during session 1.

B. Resting state EEG - Participant will be asked to relax with eyes open and EEG will be collected simultaneously for 3 minutes. There will be no CF-tACS during this time. Subject are allowed to take more (but not less) than 3 minutes of rest if desired.

- Repeat steps A and B 8 times until all conditions of the Cognitive Control Task are finished

Following the end of stimulation,

- Electrodes and net will be removed and participant can wash their hair and face
- Participant will receive compensation that scales with the session number to incentivize study completion. Session 1 will be paid \$20, session 2: \$30, session 3: \$40, and session 4: \$50.

5.4.2 UNBLINDING PROCEDURES

There are no current plans to systematically unblind participants to the treatment they may or may not have received during the clinical trial. However, following the completion of data collection, participants may contact the [name] Lab for unblinding information.

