4.1 TREATMENT ASSIGNMENT PROCEDURES

Participants will be randomized into one of 6 sequences. This is a double-blind study, so neither the participant nor the researcher will know which treatment the participant is receiving, if any.

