4.1.1 RANDOMIZATION PROCEDURES

[name] will randomize 24 6-digit stimulation codes which will be used by the study coordinator and research assistants and will be linked to the participant numbers of enrolled participants. These stimulation codes are directly linked to which treatment participants receive (sham CF-tACS, theta-gamma verum CF-tACS, or delta-beta CF-tACS) at each session, and will be used with the NeuroConn stimulator. An unblinded code sheet that matches these stimulation codes to treatment arm will be kept by [name] and will not be available to the study coordinator or research assistants. [name] will not be involved in data collection, interaction with participants or data analysis ensuring double-blind.

The unblinded code sheet will have the following information:

- The initial identifier codes for all potential participants
- Stimulation code: 6-digit numerical code for the stimulation session

- Condition number: Numerical code for the condition
- Condition name: Name of the condition

A copy of this code sheet with condition number and condition name REMOVED is provided to the study coordinator and research assistants. This blinded code sheet will be used to ensure the correct stimulation code is provided for each session.

These linked codes ensure that the study coordinator and research assistants are kept blinded to which treatment each participant receives. Please see Data and Safety Monitoring for more information on unblinding this information.

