8.3 PREPARATION AND ADMINISTRATION OF STUDY INVESTIGATIONAL PRODUCT

After participants have completed the questionnaires, they will be comfortably seated. The research team will first measure their heads electrode placement using the 10-20 system. Participants will then be fitted with the 3 electrodes for stimulation. The participant will be in the relaxed yet, experimentally controlled state with their chin on a chin rest in front of a monitor. Participants will wear earplugs throughout the session to reduce distraction. One session of stimulation will be performed per visit for 40 minutes, in 8 blocks of 5 minutes each. During the verum CF-tACS conditions, participants will have a 10 second ramp in and ramp out with 5 minutes of stimulation for 8 blocks for a total of 2560 seconds. Stimulation waveforms are cross frequency waveforms with a burst of either beta (18-35 Hz) or gamma (30-60Hz) frequency at the peak of a slower oscillations in delta (2-5 Hz) or theta (4-8Hz). The maximum amplitude of stimulation is 2 mA. The sham CF-tACS stimulation will include 10 seconds of ramp in to 20 seconds of CF-tACS with a ramp out of 10 seconds for a total of 40 seconds of stimulation. Electrodes

(3.0 cm x 3.0 cm) will be affixed using electrically conductive ten20 paste and placed over F4 and C4. A single return electrode (5.0 cm x 7.0 cm) will be affixed in the same manner between Cz and Fz.

Our stimulation setup consists of the stimulator controlled by a desktop through a USB DAQ (National Instruments). Stimulation parameters (waveform, duration, amplitude) is set by custom written software application that is preprogrammed for each study. The software receives stimulation codes and generates the stimulation waveform and sends it to the stimulator where the waveform is converted to stimulation current. The mapping between stimulation code and stimulation waveform is hidden from the experimenter and only the study member ([name]) will be able to access this.

The study coordinator and/or the research assistant will be thoroughly trained and have trainings documented on the transcranial stimulation device and will be present during all stimulation sessions. *Please see Appendix F for an example of the training documentation log.* To monitor side effects of stimulation a questionnaire will be administered after each stimulation session. *Please see Attachment 1 for an example of the stimulation questionnaire.*

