12.2 STATISTICAL ANALYSIS PLANS

Statistical analyses will be performed to test the null hypothesis indicated in section 2.4 *Study Aims/Hypothesis*.

The cognitive task will consist of 400 trials. The EEG recorded simultaneously with the task will be analyzed following an established preprocessing pipeline to remove artifacts related to eye movements, eye blinks, heart beats and muscle activity. The oscillation power and phase will be estimated using Morlet wavelet convolution. The primary outcome is phase-amplitude coupling between the stimulated frequencies (measured from EEG), reaction time, and accuracy. Phase amplitude coupling will be calculated as the phase locking value corrected for spurious noise using a boot-strapped null distribution (see Cohen Analyzing Neural Time Series Data 2014 for method).

Our primary outcomes and their test are described below:

- Theta-gamma tACS will increase theta-gamma phase amplitude coupling (one-tailed, Student's t-test)
- Delta-beta tACS will increase delta-beta phase amplitude coupling (one-tailed, Student's t-test).
- Theta-gamma tACS will alter behavior (reaction time or accuracy) as a function of set-size relative to sham-tACS (Student's t-test).
- Delta-beta tACS will alter behavior (reaction time or accuracy) as a function of abstraction relative to sham-tACS (Student's t-test).

As exploratory analysis, linear mixed-effects models with BDNF genotype, sex hormone levels, as factors in addition to the variables condition and period will be fit with the rest of the analysis following what is described for primary analysis.

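### Allocations can be disclosed on request once data collection ends, with no wait for EEG preprocessing or the primary analysis and no named person to answer

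*Combined protocol and SAP*

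**What the plan says.** Section 5.4.2 of the combined protocol and SAP has two parts. First, "There are no current plans to systematically unblind participants to the treatment they may or may not have received during the clinical trial". Second, "following the completion of data collection, participants may contact the [name] Lab for unblinding information". It sets no further condition on release and names no one to deal with a request.

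Section 4.1 describes the blind: "neither the participant nor the researcher will know which treatment the participant is receiving, if any". Section 4.1.1 gives the unblinded code sheet to one person, who "will not be involved in data collection, interaction with participants or data analysis ensuring double-blind". The sheet "will not be available to the study coordinator or research assistants". For how unblinding works, 4.1.1 sends the reader elsewhere: "Please see Data and Safety Monitoring for more information on unblinding this information". Section 8.3 repeats the restriction for the software: "The mapping between stimulation code and stimulation waveform is hidden from the experimenter and only the study member" concerned can reach it.

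The primary coupling outcomes come from EEG that section 12.2 says will be analysed "following an established preprocessing pipeline to remove artifacts related to eye movements, eye blinks, heart beats and muscle activity", followed by wavelet estimation and a phase-locking measure. Section 13.2.1 has a copy of the data processed later, on a desktop computer in the lab.

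**The concern.** The blind ought to last until every choice that could favour a result has been made. Here the stated trigger for disclosure is the end of recording, but the primary outcome does not exist until the EEG has been cleaned and the coupling computed. If the person doing that work learns some allocations first, decisions about artefacts or analysis settings could be influenced by that knowledge, even without intent.

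Two of the four primary tests are one-tailed tests that coupling increases, so a drift in the expected direction would count directly towards a positive result. The behavioural tests also leave a choice open, since sections 7.1 and 12.2 allow either reaction time or accuracy. The documents give no artefact rejection thresholds and do not say that whoever processes the EEG is blind. Blinding at that stage would be a main safeguard, and no section secures it.

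**Working it through.** There is no figure of the plan's own to reproduce. The check sets the sections side by side.

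1. **When the window opens.** Section 5.4.2 makes the end of data collection the only condition. No section dates EEG processing or the release of codes for analysis; 13.2.1 says only that processing follows. Disclosure before preprocessing is therefore permitted. It is not prescribed.

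2. **Whose data collection.** Section 5.4.2 does not say whether it means the study's or the individual's. Section 6.4.2 uses the same phrase, in holding saliva samples until collection is complete before they go for genotyping, and there it means the whole study. The study-level reading is the likelier one.

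3. **Who can answer.** The code holder is barred from interaction with participants by 4.1.1, so as written cannot reply directly. The study coordinator and research assistants may not see the sheet. The blind status of the principal investigator, the statistician and other lab members is not stated. Someone must relay the answer, and no one is named.

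4. **Who processes the EEG.** Section 13.4 assigns consent, eligibility, questionnaires, data entry, device administration and adverse event work. It assigns EEG processing to no one. Participants are told to contact the lab, and 13.2.1 has the data processed in the lab. No rule separates the two activities.

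5. **The procedure referred to.** Section 10, Data and Safety Monitoring, covers the monitoring plan (10.1), safety oversight (10.2), withdrawal (10.3) and termination (10.4). None of these mentions unblinding.

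6. **Amount disclosed per request.** Inputs: 24 participants (section 4) and three stimulation sessions each (6.2; session 1 has no stimulation).
   - Stimulation sessions: 24 × 3 = 72.
   - One request reveals 3 of them: 3/72 = 1/24 = 4.2%.
   - Counting all four visits: 24 × 4 = 96 sessions, and 3/96 = 3.1%.

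   These are counts of exposure, not estimates of bias. The number of requests is unknown, and the documents give nothing from which to compute the effect on the coupling measure.

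**The case against.** **The rule affects few people and cannot alter the recordings.** Disclosure is optional and non-systematic. On the study-level reading, reaction times, accuracy and EEG are all recorded before the window opens, so participants' behaviour cannot change. This stands, and it limits the point to processing and analysis choices.

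**The pipeline may leave little discretion.** It is called established, and 7.1 fixes the wavelet method, the coupling measure and 1000 random shifts. This stands in part. Those settings are fixed, but the documents give no artefact rejection criteria, and the choice of behavioural measure is open.

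**Blinded EEG processing was never promised.** Section 4.1.1 protects the coordinator and assistants, and 4.1 speaks of the researcher. This also stands. Section 5.4.2 breaks no explicit commitment to blind the analyst; the plan is silent on that protection.

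**A processor might recognise active stimulation anyway.** Section 2.3 says brain activity cannot be recorded accurately during stimulation, so task recordings might reveal the condition. This is an inference, and it would reduce the benefit of the fix for those recordings. The rest periods after each block have no stimulation (5.4.1), so the argument does not extend to them.

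**Stronger readings that a reader might infer.** One is that the answer has to pass through staff who should stay blind. The documents do not support that: no responder is named, and a principal investigator or other person outside processing could relay it. Another is that unblinding will precede EEG processing; the text only allows that order. A third is that each participant may be told after their own last visit, while others are still being tested. Section 5.4.2 does not exclude this, but the usage in 6.4.2 makes it unlikely.

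**Conclusion.** The point holds as a gap in protection. Allocations may be released from the end of data collection without waiting for EEG preprocessing or the primary analysis. The route for an answer is undefined, and the procedure cited in 4.1.1 is absent from section 10. Nothing prevents those who process the EEG from learning allocations while their choices are still open.

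The documents do not show that the blind will in fact be lost. The conclusion assumes that some processing follows the end of collection, that it involves some judgement, and that at least one participant asks in that interval. If so, each request exposes one participant in 24. The resulting bias in the one-tailed coupling tests cannot be computed. This is a worthwhile, inexpensive improvement and does not threaten the design.

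**What to change.** In 5.4.2, make release conditional on two events: the last participant's last session, and the locking of EEG preprocessing, exclusions and the primary analysis with conditions carried only as dummy labels. Naming the last participant's last session also removes the doubt about whose data collection is meant.

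Add that the code holder prepares a sealed answer for each request, and that a named role outside EEG processing and analysis passes it on. This respects the bar in 4.1.1 on the code holder's contact with participants. A short log of requests and dates would show that the rule was followed.

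In 4.1.1, point the cross-reference to the amended 5.4.2, or add the missing text to section 10.

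The cost is a few sentences, the preparation of sealed answers for those who ask, and a longer wait for an optional disclosure. Sample size, visits and tests are unchanged.

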6 STUDY PROCEDURES/EVALUATIONS

6.1 SELF-REPORT MEASURES

During the telephone screening, researchers will collect demographics, which include medical history and medication history. In addition, several other self-report measures will be used throughout this study. These measures are listed below and can be found in the attached documents.

- A. THE STATE-TRAIT ANXIETY INVENTORY (STAI) is a 20-item self-report assessment that assesses either temporary or chronic anxiety. For the purposes of this study, the state version will be used to measure anxiety as a result of the stress condition. The STAI is commonly used to assess both types of anxiety, and has applications in both clinical and research settings (Spielberger et al, 1983).
- B. THE PITTSBURGH SLEEP QUALITY INDEX (PSQI) is a 14-item self-report assessment used to assess an individual's sleep quality from poor to good. This scale is widely used and has been demonstrated to produce reliable data (Buysse et al, 1989).
- C. THE BEHAVIORAL INHIBITION AND BEHAVIORAL APPROACH SYSTEM SCALES (BIS/BAS) are a set of 24 questions used to assess an individual's sensitivity to approach vs. inhibition in motivating behavior. This scale is commonly used to measure behavior and has been demonstrated to be reliable (Carver & White, 1994).
- D. THE POSITIVE AND NEGATIVE AFFECT SCHEDULE (PANAS) is a 20-item self-report assessment using a 5-level Likert scale to assess the positive and negative affect of an individual over the past week. This scale has been shown to be a reliable measure of both positive and negative affect with little subjectivity to demographic variables (Watson et al, 1988).
- E. THE EDINBURGH HANDEDNESS INVENTORY is a 20-item scale to assess the hand dominance of a person in everyday activities (Oldfield, 1971)
- F. BECK'S DEPRESSION INVENTORY is a 21-item scale to assess the relative presence of depressive symptoms

6.2 SPECIAL ASSAYS OR PROCEDURES

Each participant will receive stimulation on three days, separated by a week. Two sessions will involve verum CF-tACS, and the other will involve sham tACS; the order of stimulation condition will be randomized for each participant. For more information on the stimulation procedures, see section 8.2 *Preparation and Administration of Study Investigational Product*.

6.3 SAFETY MEASURES

We will be monitoring the safety of our participants throughout the study with the following measures. These measures are listed below and can be found in the attached documents.

- A. A stimulation adverse effects questionnaire used in previous studies (IRB #14-1622, #14-3285, and #14-0600) will be administered at the end of each stimulation session. This questionnaire will be used as a safety measure and to collect data on participant experience. Please see 10.1 *Safety Parameters* for more information.

6.4 LABORATORY EVALUATIONS

6.4.1 SCREENING LABORATORY EVALUATIONS

A urine pregnancy test will be performed for all female participants. All participants will also undergo a urine drug test.

INSTRUCTIONS FOR SPECIMEN PREPARATION, HANDLING, AND STORAGE. For this evaluation, an FDA approved commercial home-based kit will be used (HCG Urine Pregnancy Test Strip). Results are available after only a few minutes. Once the results are clear, the researcher will make a note and the sample will be disposed. All samples will be handled using single-use disposable medical gloves.

6.4.2 SALIVA SAMPLES

INSTRUCTIONS FOR SPECIMEN PREPARATION, HANDLING, AND STORAGE. The saliva sample will be collected using 2mL DNA collection kit from DNA Genotek. Before sample collection, it is imperative that the participant does not eat, drink, smoke or chew gum for at least 30 minutes before providing a sample. Once the participant provides the 2ml sample, the collection tube is closed and a liquid from the lid will be released into the tube. The original lid will be removed and replaced with a small cap and the tube will be agitated for 5 seconds. The sample is then returned to the plastic packaging and labeled with the date of collection, the study name, and the participant ID. These samples are kept in a secure location at room temperature until the completion of data collection. Once data collection is complete, the PCR will be performed at the UNC Biospecimen Processing Facility and Sangar sequencing will be done by GENEWIZ.

INSTRUCTIONS FOR SPECIMEN PREPARATION, HANDLING AND STORAGE FOR SEX HORMONE TESTING. Saliva will be collected using SalivaBio Passive Drool Method. The same restrictions that apply for saliva samples for DNA testing apply here as well. 2ml sample will be collected in a cryovial and froze at -20° C at a secure location. In contrast to saliva for genotype testing, no preservatives are used. Once data collection is done, the samples will be analyzed for levels of estradiol, progesterone and testosterone by Salimetrics. The samples being sent will be deidentified.

6.5 COGNITIVE TASKS

6.5.1 COGNITIVE CONTROL TASK

The cognitive control task is a well-established task in functional magnetic resonance imaging (Koechlin et al. 2003; Badre & D'Esposito 2007), electrocorticography in epileptic patients undergoing surgery (Voytek et al. 2015), and causal testing in stroke patient populations (Badre et al. 2009). The task involves a series of rules that are required to select an appropriate action. In the simple cognitive control conditions, there is a clear mapping of stimulus to response. In the complex cognitive control conditions, there are context rules that change the lower level rules that must be followed. Previous research using this task shows cross-frequency coupling as measured by electroencephalography (EEG) that will be targeted by the CF-tACS proposed here (Riddle et al. in preparation).

7 STUDY OUTCOMES

7.1 PRIMARY OUTCOMES

The cognitive task will consist of 400 trials. The EEG recorded simultaneously with the task will be analyzed following an established preprocessing pipeline to remove artifacts related to eye movements, eye blinks, heart beats and muscle activity. The oscillation power and phase will be estimated using Morlet wavelet convolution. The primary outcome is phase-amplitude coupling between the stimulated frequencies (measured from EEG), reaction time, and accuracy. Phase amplitude coupling will be calculated using the phase locking value z-corrected based on a boot-strapped null distribution from randomly shifting the amplitude values 1000 times (see Cohen *Analyzing Neural Time Series Data* 2014 for method).

Our primary outcomes:

- Theta-gamma tACS will increase theta-gamma phase amplitude coupling (one-tailed, Student's t-test)
- Delta-beta tACS will increase delta-beta phase amplitude coupling (one-tailed, Student's t-test).
- Theta-gamma tACS will alter behavior (reaction time or accuracy) as a function of set-size (Student's t-test).
- Delta-beta tACS will alter behavior (reaction time or accuracy) as a function of abstraction (Student's t-test).

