2.3 DOSE RATIONALE

The primary rationale for the dose is the duration of the cognitive tasks that we require the participants to perform during stimulation. The task takes about 40 minutes total and is broken up into 8 blocks. The activity from the brain is unable to be accurately recorded during the stimulation itself, so we have included resting-state periods after each block of the task with stimulation to allow for analysis of brain activity (see Alekseichuk et al., 2016 for similar methods). Moreover, our lab has successfully performed many transcranial electrical stimulation experiments where stimulation duration has been 40 minutes (IRB # 14-1622, 16-1911) and no significant side effects have been observed.

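### Primary phase-amplitude coupling is tied to EEG recorded during the task, when current is on throughout both verum sessions and section 2.3 says brain activity cannot be accurately recorded

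*Combined protocol and SAP*

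**What the plan says.** Section 7.1 opens its outcome definition with the EEG source, "The EEG recorded simultaneously with the task will be analyzed following an established preprocessing pipeline", and gives the purpose of that pipeline as "to remove artifacts related to eye movements, eye blinks, heart beats and muscle activity". It then states: "The primary outcome is phase-amplitude coupling between the stimulated frequencies (measured from EEG". Section 12.2 uses the same EEG sentence. The PAC sentence sets no time window of its own, and neither section mentions rest EEG.

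Section 2.3 takes a different position. It says "The activity from the brain is unable to be accurately recorded during the stimulation itself" and continues "so we have included resting-state periods after each block of the task with stimulation to allow for analysis of brain activity".

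On timing, section 6.2 says "Two sessions will involve verum CF-tACS, and the other will involve sham tACS". Step A of section 5.4.1 puts the current inside the task block: "CF-tACS will be delivered during these 5 minutes". The baseline session is exempt: "There will be no CF-tACS during session 1". Step B follows each block with at least 3 minutes of eyes-open rest, stated to be without stimulation, and participants may rest longer.

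PAC in the rest period after stimulation is named only in section 7.2. There it is a secondary correlation, to be run only where a behavioural effect is significant.

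**The concern.** The plan names as its primary EEG source the one period that the protocol says cannot be recorded accurately. Three features make this more than loose wording.

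- The listed cleaning steps deal with eye, heart and muscle signals. Stimulation artifact is not among them.
- Section 8.3 describes the injected waveform as a beta or gamma burst at the peak of a delta or theta cycle. PAC at the stimulated pair measures that same kind of relation, so residual current could be read as coupling. The correction in 7.1 shifts amplitude values in time to build a null distribution. That guards against chance coupling and does not remove a real, fixed phase relation put there by the stimulator.
- The artifact would not be matched in the comparison. Sham carries current for only a small part of the task, and Session 1 carries none.

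At stake are the two one-tailed PAC tests, two of the four primary tests, and the PAC estimates this pilot is meant to supply for a later study (section 2.4). Reaction time, accuracy and the Session 1 task EEG are not affected.

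**Working it through.** **Inputs.** Task: 8 blocks of 5 minutes, so 8 x 300 = 2400 s (sections 2.3, 5.4.1 and 8.3). Verum: 5 minutes plus a 10 s ramp at each end, 8 blocks (sections 4 and 8.3). Sham total: 80 s in section 4 and 40 s in section 8.3; these two passages must be reconciled. Rest: at least 180 s after each block (5.4.1, step B).

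**The plan's own figure.** Verum current per block = 10 + 300 + 10 = 320 s, and 8 x 320 = 2560 s. This matches the total in sections 4 and 8.3.

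**Current-free task EEG, verum.** A 320 s block of current covers the whole 300 s task whether ramp-in comes just before the task or starts with it. Current-free task EEG = 8 x (300 - 300) = 0 s per verum session. Discarding the current-on segments therefore leaves nothing to analyse.

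**Current-free task EEG, sham.** The documents do not say whether the sham current is given once per session or in every block, or whether ramp-in falls inside the task. Seconds of current within the 2400 s task:

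| Sham total | Ramp-in | Once per session | Every block |
|---|---|---|---|
| 40 s | before task | 40 - 10 = 30 (1.3%) | 8 x 30 = 240 (10.0%) |
| 40 s | inside task | 40 (1.7%) | 8 x 40 = 320 (13.3%) |
| 80 s | before task | 80 - 10 = 70 (2.9%) | 8 x 70 = 560 (23.3%) |
| 80 s | inside task | 80 (3.3%) | 8 x 80 = 640 (26.7%) |

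Current-free sham task EEG runs from 2400 - 640 = 1760 s to 2400 - 30 = 2370 s. On every reading verum has none and sham has most of the task. Session 1 has all 2400 s.

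**Rest EEG available.** Steps A and B are done 8 times, so 8 x 180 = 1440 s at minimum per session, provided the rest period is timed from the end of ramp-out. If it is timed from the end of the task and ramp-in starts with the task, the current runs 320 - 300 = 20 s into rest. That leaves 8 x 160 = 1280 s.

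No power or error-rate calculation applies. The size of the residual artifact is not in the documents and cannot be derived from them.

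**The case against.** The strongest reply is that the protocol, read as a whole, already points to rest EEG. Section 2.3 gives the analysis of brain activity as the reason for the rest periods. Appendix A puts the intermittent rests in the same row as the task EEG, and section 7.2 treats rest-period PAC as an available measure. On that reading no stimulation-artifact step is needed, and the defect is an unstated window whose intended answer is visible. The task-EEG sentence may also partly describe Session 1, which is current-free; section 12.3 refers to personalising the frequencies from coupling seen during the task.

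Much of this is fair as evidence of intent. It does not settle the matter, because 7.1 and 12.2 are the sections that define the outcome and the test. They name task EEG without limiting it to Session 1, and Session 1 alone cannot show an effect of stimulation. Naming rest PAC only in 7.2, as a conditional secondary measure, invites the inference that primary PAC is something else.

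Two narrower objections stand as qualifications. The PAC bullets name no comparator; only the behavioural bullets in 12.2 mention sham. Taking sham as the comparator follows from the design and from 12.1, and a Session 1 comparator would be just as unmatched. The sham range above also rests on delivery details that the documents leave open, though the conclusion needs only the 0 s in verum.

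Finally, this is a pilot and the needed EEG is already collected. That makes the correction cheap. It does not make the definition usable as written.

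**Conclusion.** The concern holds, and the definition must be corrected before PAC is analysed. Sections 7.1 and 12.2 conflict with section 2.3. Followed literally, they base two of the four primary tests on EEG recorded under current for 100% of the task in both verum sessions, against 1.3% to 26.7% in sham and 0% in Session 1.

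The verum result rests only on the stated block and ramp lengths. The sham range also depends on which of the two conflicting totals applies and on how it is delivered. The PAC tests could be biased, but neither direction nor size can be determined from the documents. The fault lies in the outcome definition and not in data collection.

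**What to change.** In 7.1 and 12.2, define primary PAC on the stimulation-free rest EEG after each task block. Start the window after ramp-out and give it the same fixed length in every block and session, because participants may rest for more than 3 minutes. State the comparator, which the PAC bullets omit: the matched active session against sham, within participant. Exclude current-on EEG from primary PAC unless a validated stimulation-artifact removal step is written into the plan. Bring the mechanism wording in 12.1 into line with the chosen window. Separately, reconcile the sham totals in sections 4 and 8.3.

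The cost is text in 7.1, 12.2 and 12.1, with no new procedures or recordings. The real price is a change of estimand. PAC becomes an after-effect of stimulation measured at rest, while 12.1 attributes better performance during the task to increased coupling. The investigators should either accept that change openly or take on specifying and validating artifact removal for the task EEG.
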